In the open-label phase (Part 2, Part 3, and Part 4), only the subjects whom the investigator considers eligible for the study will be injected. The eligibility is evaluated at a study visit after Week 12 (V5. If a subject does not meet the criteria at V5, the eligibility is evaluated at QRV (Qualification for Retreatment Visit). Subjects are considered to be eligible if the following criteria are all satisfied:

- 1) At least 12 weeks (84 days) have passed since the preceding dose
- 2) Among the finger, wrist or elbow flexors, 2 flexors have at least 2 on the MAS (except only the finger and wrist flexors of 2 on the MAS)
- 3) Subject who request the injections
- 4) Subjects whom an investigator considers an injection of 400 units of the product is appropriate
- 5) Subjects who have not experienced serious adverse events (SAE) associated with the injections of the product

If subjects meet the criteria of the above 1) to 5) at V5 or QRV, body weight measurement, ECG, pulmonary function test, and pregnancy test will be performed to evaluate the following items. If subjects meet the following 6) to 8), the subjects will move forward to V1.

- 6) Body weight ≥ 40 kg
 - 7) Subjects who the investigator considers there are no unacceptable safety concerns [potential for serious adverse events, electrocardiogram (ECG) or abnormal pulmonary function value*] due to 400 U of BOTOX
- * This study will use SpO₂ (oxygen saturation) as a parameter of pulmonary function. A subject who has a $\geq 3\%$ reduction from the pre-injection SpO₂ (Day 1) in post-injection SpO₂ or whose SpO₂ value is $< 95\%$ should be referred to a pulmonologist. A subject with pulmonary dysfunction due to study treatment also should be referred to a pulmonologist. If the subject is considered by the pulmonologist to have no concerns about pulmonary function, the investigator should carefully consider whether to start the study treatment.
- 8) Women of childbearing potential who have negative pregnancy test result in urine

A pulmonary function test must be performed at V5 even if subjects do not meet the above 1) to 5) in accordance with the study operation schedule (SoA).

2. SCHEDULE OF ACTIVITIES (SoA)

Compliance with the protocol (including the list of the study conduct schedule) is important and required to conduct the study. Therefore, exemption or discharge cannot be allowed, except but emergency safety concerns arise.

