6.1. Inclusion Criteria

6.1.1. Screening Phase (Day -28 to Day -1)

In the screening phase, subjects eligible for enrolment in the study must meet all of the following criteria. Laboratory parameters should be measured by 7 days (± 3 days) before initial injection (Day 1).

Age

1. Between 20 and 80 years of age at the time of informed consent (ICF).

Subjects and Characteristics of the Disease

2. Patients with at least a 3-month history of upper limb spasticity after the most recent stroke
3. Patients who have spastic symptoms in the finger (including the thumb), wrist, and elbow flexors whom the investigator considers the injections of 400 units of the product is necessary for the upper limb based on the muscle spasms and the symptoms of the patient
4. Patients who have a previous treatment history of 240 units of the product for the upper limb at least 16 weeks before screening (refer to [Table 3](#) for muscles in the upper limbs)
5. Patients who meet following criteria on MAS at screening (Test position: sitting)
 - At least 3 in for the elbow flexors
And
 - At least 2 in the finger or wrist flexors
6. Patients who have severe upper limb spasticity, which deserves to be treated with 400 units of the product in the divided dose and was previously injected 240 units of the product
7. Patients whom the investigator considers that enrolment in the study poses no problems based on the laboratory data results at screening
8. Patients who are free from a history of acute decreased lung function (hospitalization with aggravated asthma/COPD, pneumonia, or signs of pneumonia, or abnormal reactive airway diseases suggested on X-rays) within the last 3 months at screening and have stable pulmonary function (SpO_2 value is $\geq 95\%$)

Body Weight

9. Body weight ≥ 40 kg at screening

Sex

10. Male or female

a. Male Subjects

Male subjects must content to use highly effective contraceptive methods, which are shown on attachment 5 of the protocol in detail during the study period, and sperm donation must be avoided.

b. Female Subjects

Female subjects who are not pregnant or lactating are considered eligible (refer to attachment 5) if at least one of the following criteria is met:

- i) Non-childbearing potential based on the definition on attachment 5

- ii) Women of childbearing potential who content to follow the guidance about contraception on attachment 5 during the study period and at least for 3 months after the last dose of the product.

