- iii) No plan of pregnancy during the study period

Informed Consent

11. Patients who have ability to sign their name on the ICF, following the description on attachment 3, adhering to the requirements and limitations described on the ICF and the protocol.

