A female study subject of childbearing potential can participate in this study if she agrees to use any of the extremely effective methods of contraception shown in Table 11 continuously and accurately. Among the methods of contraception shown in Table 11, those deleted with strikethrough lines have neither been approved nor been accepted in Japan.

Table 11 Extremely effective methods of contraception

User-dependent extremely effective methods of contraception ^a Their annual failure rates are below 1% if they are used continuously and accurately.
Contraception by mixed (estrogen and progestogen-containing) hormone preparation (inhibit ovulation) ^b 
 • Oral • Intravaginal • Transdermal
Contraception by only progestogen-containing hormone preparation (inhibit ovulation) ^b 
 • Injection
User-independent extremely effective methods of contraception

 • Contraception by only progestogen-containing implantable hormone preparation (inhibit ovulation)^b • Intrauterine device (IUD) • Intrauterine system (IUS) • Bilateral tubal occlusion
Male partner's vasectomy (If her male partner has been vasectomised, it is an extremely effective method of contraception for a woman of childbearing potential if that partner is the only man with whom she has a sex and it has been confirmed that he is sterile. Otherwise, he/she must use other additional extremely effective method(s) of contraception.)
Having no sexual relations (If the subjects decide to refrain himself or herself from having a sex of the opposite sex for the entire period when there is a risk of the investigational product, abstinence is deemed to be an extremely effective method of contraception. However, the credibility of abstinence needs to be evaluated during the study period and from the perspectives of the subject's normal favourable lifestyle.)

Notes:

- a. The usual failure rate is different from the rate when contraception is used continuously and accurately. The subjects should use the methods of contraception that match with regulations concerning the methods of contraception for study subjects in each country.

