- b. The efficacy of contraception by hormone preparations may decrease as a result of the interaction with the investigational product. In that case, the subject should use two extremely effective methods of contraception during the treatment period and at least for 3 months after the last dose of the investigational product.

Pregnancy test

- A woman of childbearing potential can be enrolled to this study only if it is confirmed that she is negative in a highly sensitive serum pregnancy test along with her menstrual period.
- Pregnancy test should be performed if no menstruation occurred or she is suspected to be pregnant.
- Analysis should be performed according to the package insert using a testing kit provided by GSK.

Collection of pregnancy information**If a male study subject's partner becomes pregnant**

- Investigator will attempt to collect pregnancy information on any male participant's female partner of a male study participant who becomes pregnant while participating in this study. This applies only to participants who receive study treatment.
- After obtaining the necessary signed informed consent from the pregnant female partner directly, the investigator will record pregnancy information on the appropriate form and submit it to GSK within 2 weeks of learning of the partner's pregnancy.
- Partner will also be followed to determine the outcome of the pregnancy. Information on the status of the mother and child will be forwarded to GSK
- Generally, follow-up will be no longer than 6 to 8 weeks following the estimated delivery date. Any termination of the pregnancy will be reported regardless of fetal status (presence or absence of anomalies) or indication for procedure.

Female Participants who become pregnant

- Investigator will collect pregnancy information on any female participant, who becomes pregnant while participating in this study.
- Information will be recorded on the appropriate form and submitted to GSK within 24 hours of learning of a participant's pregnancy.
- Participant will be followed to determine the outcome of the pregnancy. The investigator will collect follow up information on participant and neonate, which will be forwarded to GSK Generally, follow-up will not be required for longer than 6 to 8 weeks beyond the estimated delivery date.
- Any termination of pregnancy will be reported, regardless of fetal status (presence or absence of anomalies) or indication for procedure.

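### Inclusion criterion 10b lets a woman of childbearing potential enter solely because she plans no pregnancy, although Appendix 5 makes contraception the condition for taking part

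*Protocol*

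**What the plan says.** Section 6.1.1 (screening), criterion 10b, deals with female subjects. Women who are not pregnant or lactating "are considered eligible (refer to attachment 5) if at least one of the following criteria is met". The list has three items at the same level:

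- i) non-childbearing potential as defined in Appendix 5;
- ii) childbearing potential, with agreement to follow the Appendix 5 contraception guidance during the study and for at least 3 months after the last dose;
- iii) "No plan of pregnancy during the study period".

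Item iii) is not limited to any childbearing status and carries no contraception condition.

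Appendix 5 (section 12.5, paragraph on female subjects) says that a woman of childbearing potential "can participate in this study if she agrees to use any of the extremely effective methods of contraception" listed in Table 11. It makes no exception for a woman who merely plans no pregnancy. Table 11 includes abstinence.

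The criterion for men, 10a, has no alternative route: "Male subjects must content to use highly effective contraceptive methods".

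The wording of 10b is the same in the original protocol, Amendment 1 and Amendment 2, so it is current text.

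**The concern.** Under a rule that one item suffices, item iii) is a complete route to eligibility. A woman of childbearing potential who refuses all contraception but says she plans no pregnancy satisfies 10b as printed. Appendix 5 points the other way for the same woman. A site checking section 6 and a monitor checking Appendix 5 could reach opposite decisions, in a trial whose sections 6 and 9 allow no waivers.

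What is at stake is safety, namely fetal exposure to the product, and the consistency of an eligibility rule. Entry through iii) alone also bypasses the commitment to contraception for 3 months after the last dose. In section 6.1.1 that commitment stands only in item ii). The female paragraph of Appendix 5 gives no duration, and the 3-month period there appears only in the Table 11 note on interaction with hormonal methods.

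**Working it through.** The protocol gives no figure to reproduce; the check is one of logic.

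**Inputs**

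- Criterion 10b (section 6.1.1): not pregnant or lactating, AND (i OR ii OR iii).
- Appendix 5 (section 12.5): a woman of childbearing potential takes part if she agrees to a Table 11 method. This is the contraception content of item ii).

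**Case examined.** Take a woman of childbearing potential who is not pregnant or lactating. Item i) is then false, so 10b reduces to ii OR iii, while Appendix 5 reduces to ii.

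| ii) agrees to contraception | iii) plans no pregnancy | 10b as written | Appendix 5 | Agree? |
|---|---|---|---|---|
| no | no | not met | not met | yes |
| no | yes | **met** | **not met** | **no** |
| yes | no | met | met | yes |
| yes | yes | met | met | yes |

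The sections conflict in 1 of 4 combinations: she declines every Table 11 method, abstinence included, and plans no pregnancy.

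**Effect of each possible correction**

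- *(i OR ii) AND iii:* the no/yes row becomes not met, which removes this conflict. The yes/no row also becomes not met, so a woman who agrees to contraception yet plans a pregnancy is now excluded. Appendix 5 alone would not exclude her.
- *Delete iii):* 10b becomes i OR ii, which reduces to ii here and matches Appendix 5 in all four rows.

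**Other safeguards.** At enrolment a woman of childbearing potential must be "negative in a highly sensitive serum pregnancy test" (Appendix 5). Before each open-label injection the retreatment criteria (Synopsis and section 5.1.3.1) admit only "Women of childbearing potential who have negative pregnancy test result in urine". The same criteria require "At least 12 weeks (84 days) have passed since the preceding dose", so these retreatment tests come 84 days or more after the previous injection. They detect a pregnancy that may already have been exposed; they do not prevent one.

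**The case against.** The strongest reply is that 10b does not act alone. All criteria in section 6.1.1 must be met, and criterion 11 covers "adhering to the requirements and limitations described on the ICF and the protocol". A woman who rejects the Appendix 5 requirement could be said to fail criterion 11. The opening of 10b also refers to Appendix 5, section 6 forbids enrolling a subject when a deviation is expected, and section 9 rules out waivers. Further, Appendix 5 is phrased as a condition under which she can take part, not as an explicit prohibition.

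Much of this stands as evidence of intent: the stricter rule is plainly what was meant. It does not repair the text. Criterion 11 is general and does not say which of two conflicting requirements governs. The reference to Appendix 5 leaves the connector unchanged. No precedence rule favours the appendix; indeed Appendix 2 sends the reader back to section 6 for inclusion and exclusion criteria. If agreement to a method were not necessary, neither Appendix 5 nor item ii) would have any function for a woman who plans no pregnancy.

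Two further points are fair. First, testing is wider than enrolment and retreatment: Table 1 schedules a test on Day 1, Appendix 5 asks for one when menstruation is missed or pregnancy is suspected, and section 8.2.4 requires withdrawal on pregnancy. These reduce the consequence without replacing contraception. Second, criterion 10a is imperfect evidence of intent, because Appendix 5 ties male contraception to having a partner of childbearing potential, whereas 10a applies it to all men.

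**Conclusion.** The concern holds. Criterion 10b, followed as written, admits a woman whom Appendix 5 does not, in 1 of the 4 combinations of items ii) and iii). That is a count of logical cases, not of patients. The protocol gives no basis for estimating how many women fall there, and the number may be zero.

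The conclusion rests on reading the three items as parallel alternatives, which the numbering and connector support, and on reading the Appendix 5 condition as necessary, which is clear by implication though not stated as a prohibition. There is no effect on sample size, power or the primary analysis. Because this is an operative safety criterion and the correction is simple, it should be corrected.

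**What to change.** Change criterion 10b in one of two ways:

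- delete item iii), which makes 10b agree with Appendix 5 in every case and is the cleaner edit; or
- reword the stem so that a woman must meet i) or ii) and, in addition, iii), if the sponsor also wants to exclude a woman who accepts contraception but intends to become pregnant.

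Leave Appendix 5 as it is. Check the eligibility page of the case report form, which is not among the documents at hand, and give it the same logic. The cost is one line in a protocol amendment and, if needed, a form edit. No visits or tests are added.

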6.1.2. Day 1 (prior to injection)

Subjects eligible for enrolment in the study must meet all of the following criteria on Day 1 (prior to injection):

Subjects and Characteristics of the Disease

31. Patients who meet the following criteria on MAS score: (Test position : sitting)
- At least 3 in the elbow flexors
- And
- At least 2 in the finger or wrist flexors

Preceding Treatments and Concomitant Medications/Therapies

32. If centrally acting muscle relaxants, tetracycline antibiotics, anticholinergics, benzodiazepines, or benzamides are given, the dose and regimen must be stable at least for the last 2 months before Day 1; Patients who can maintain the same dosage and regimens at least in the blind phase after initial injection (dose reductions and discontinuation of the drugs are acceptable in the open-label phase. However, second dose increase, resumption, and or new treatment will not be performed).
33. If intrathecal baclofen is given, the dose and regimen must be stable at least for the last 1 month before Day 1; Patients who can maintain the same dosage and regimens at least in the blind phase after initial injection (intravenous bolus is not acceptable, dose reductions and discontinuation of the drugs are acceptable. However, second dose increase, resumption, and or new treatment will not be performed).
34. If antiepileptic agents are given, the dose and regimen must be stable at least for the 1 month before Day 1; Patients who can maintain the same dose and regimens at least in the blind phase after initial injection (dose reductions and discontinuation of the drugs are acceptable in the open-label phase. However, second dose increase, resumption, and new treatment will not be performed).
35. If a physical therapy, occupational therapy, or a static splint on the study involvement upper limbs is given, the frequency and treatment regimen must be stable at least for the last 3 weeks before Day 1; Patients who can maintain the same dose and regimens at least in blind phase (In the open-label phase, the frequency and treatment regimen can be changed depending on the condition of spasticity).

6.2. Exclusion Criteria

6.2.1. Screening Phase (Day -28 to Day -1)

A subject will be excluded from enrolment in this study if any of the following criteria apply in the screening phase. Measurements of laboratory parameters at screening must be completed 7 days (± 3 days) before initial injection (Day 1).

Medical Condition

1. Patients present with spasticity requiring treatment in the non-paralytic side of the upper limb
2. Patients who have fixed contracture* in the finger (upper limb), wrist, elbow or shoulder muscle, which will be involved in the study
(*Positive effects were not confirmed in the previous treatment with GSK1358820, and contracture is considered to be the main cause of limited range of motion in the joint.)
3. Patients who have medically significant capsulitis or subluxation in any one of the fingers (upper limb), wrist, elbow and shoulder, which will be involved in the study, or whom an investigator considers the complicated local signs of pain may affect the efficacy evaluation
4. Patient's upper limb spasticity is attributed to other than stroke (traumatic brain injury, spinal cord injury, multiple sclerosis, or cerebral palsy)
5. Patients who have a 2-fold higher alanine aminotransferase (ALT) level than the upper limit of normal (ULN)
6. Patients who have a 1.5-fold higher bilirubin than the ULN (If a bilirubin fractionation shows direct bilirubin $< 35\%$, a 1.5-fold higher free bilirubin than the ULN is acceptable).
7. Patients whom the investigator considers presence of a current medical history of unstable liver diseases or biliary tract diseases (the condition will be defined by development of ascites, encephalopathy, coagulopathy, hypoalbuminemia, esophageal or gastric varices, persistent jaundice or hepatic cirrhosis)

Note:

- If a patient with stable chronic liver diseases (Gilbert's syndrome, silent gallstone, and stable chronic hepatitis B or hepatitis C [Namely, hepatitis B surface antigen: HBsAg or hepatitis C virus: HCV antibody shows positive at screening or within 3 months before initiation of the study treatment] are included) meets other inclusion criteria, the patient can be enrolled in the study.
8. Patients with QTc > 450 msec or QTc > 480 msec in patients with bundle branch block
Note:
 - QT intervals corrected by the Bazett method (QTcB); QT intervals corrected by the Fridericia method (QTcF) and/or QT intervals corrected by other methods; interpretation by a machine or manual re-interpretation will be used.
 - Prior to study initiation, the correction formula which is used for the subject's inclusion/exclusion/discontinuation criteria will be determined. Namely, several different correction formulae cannot be used for calculation of QTc in each subject. In addition, the lowest QTc level cannot be used for enrolment or discontinuation of subjects of the study.

Preceding Treatments and Concomitant Medications/Therapies

9. Patients who use peripherally acting muscle relaxants (dantrolene sodium, suxamethonium chloride, pancuronium bromide, vecuronium bromide, rocuronium bromide, etc.) within 1 week of screening.
10. Patients who use antibiotic agents with neuromuscular junction inhibitory effects: Aminoglycoside antibiotic agents (streptomycin sulfate, kanamycin sulfate, gentamicin sulfate, neomycin sulfate, spectinomycin hydrochloride, etc.), polypeptides (polymyxin B sulfate), lincomycins (lincomycin hydrochloride, clindamycin), and enviomycin sulfate within 1 week of screening.
11. Patients who was diagnosed as having a malignant tumor, or have a history of a malignant tumor within the last 5 years (except completely resected basal cell carcinoma or planocellular carcinoma at least 12 weeks before screening)

Previous Experience of Participation in a Clinical Studies/Current Participation in another Ongoing Study

12. Patients who have participated in another study of an investigational product or other medical research (a clinical study of pharmacotherapy, non-pharmacotherapy, or interventional device) within 30 days before screening, or are currently participating in a study

Evaluation by Diagnosis

13. Patients who are concerned likely to have an increased risk for an underlying medical condition/neurological disease due to exposure of the product; patients who have myasthenia gravis, Eaton-Lambert syndrome, amyotrophic lateral sclerosis, or a serious disease and use of a concomitant drug which may inhibit neuromuscular function
14. Patients with antihuman immunodeficiency virus (HIV) antibody positive
15. Patients who previously experienced allergic reactions or hypersensitivity due to botulinum toxin type A, an additive agent of sodium chloride, or human serum albumin
16. Patients who were previously suspected to have neutralizing antibody production by an investigator during an injection of botulinum toxin type A
17. Patients who have a skin disease such as infection at the site to be injected
18. Patients who suffer from serious and unstable disease, which could pose problems for the safety of subjects and study procedure compliance

